2.4.4 Endpoint selection

Endpoints have been selected taking core neonatal outcome sets into account (22, 23).

Title: COLLABORATE	EDGE No: 181495	Sponsor: Imperial College London	Version: 3.0; 09/01/2026
---------------------------	---------------------------	--	---------------------------------

2.5 Summary table of objectives and endpoints

Objectives	Endpoints	Timepoints of evaluation of endpoints
Primary		

 To assess, in babies born <29 weeks gestation, the efficacy of pHDM compared with Preterm Formula when used as a supplement should there be insufficient milk from their own mother (Own Mother's Milk) on "survival to 34 weeks postmenstrual age without surgical NEC", To assess, in babies born <29 weeks gestation, if routine cow-milk based protein-carbohydrate fortification of human milk feeds (Own Mother's Milk and pHDM) compared with no routine fortification, affects "survival to 34 weeks postmenstrual age without surgical NEC" 	Survival without surgical NEC	34 weeks postmenstrual age
Secondary		

 To assess the efficacy of pHDM compared with Preterm Formula on language and cognitive development at age 2-years, and other outcomes in babies born <29 weeks gestation, when used as a supplement should there be insufficient milk from their own mother (Own Mother's Milk) 	
 Survival Surgical NEC Spontaneous Intestinal Perforation 	34 weeks postmenstrual age
	
 Bronchopulmonary dysplasia 	36 weeks postmenstrual age

Title: COLLABORATE	EDGE No: 181495	Sponsor: Imperial College London	Version: 3.0; 09/01/2026
---------------------------	---------------------------	--	---------------------------------

 To assess if routine cow-milk based protein-carbohydrate fortification of human milk feeds (Own Mother's Milk and pHDM) in babies born <29 weeks gestation affects language and cognitive development at age 2-years corrected for preterm birth, and other outcomes 	
 Survival 	Age 28 days
	
 Survival Surgery for NEC or NEC related condition after 34 weeks postmenstrual age Medical NEC Age in days to achieve an enteral intake of 150 ml/kg/day Treated retinopathy of prematurity Severe brain injury Any diagnosis of milk-curd obstruction Length of neonatal unit stay Number of episodes of bacterial or fungal bloodstream infection Number of episodes of bacterial or fungal cerebrospinal fluid infection Number of episodes of bacterial or fungal urinary tract infection Number of days of antibiotic treatment Number of days on parenteral nutrition Number of days nil by mouth Weight, length, and head circumference Z-scores Change from birth in Z-scores for weight, length, and head circumference Any breast feeding (suckling at breast) Exclusive breast feeding (suckling at breast) Receiving any expressed Own Mother's Milk Receiving exclusive expressed Own Mother's Milk Maximum serum urea, creatine, and alkaline phosphatase Health resource use 	Neonatal unit discharge (or death)

Title: COLLABORATE	EDGE No: 181495	Sponsor: Imperial College London	Version: 3.0; 09/01/2026
---------------------------	---------------------------	--	---------------------------------

	
 • Survival without moderate-severe cognitive-language impairment • Survival • Moderate-severe cognitive-language impairment • Cognitive sub-score • Language sub-score • Gross motor function • Hearing impairment • Vision impairment 	Age 2-years corrected for preterm birth
In babies with NEC surgery	
 • Drain insertion prior to surgery • Diagnosis of short bowel syndrome • Diagnosis of intestinal failure-associated liver disease • Length of bowel resected (cm) • Primary surgical procedure (ileostomy; colostomy; end-to-end anastomosis) 	Neonatal unit discharge (or death)
In babies with NEC surgery	
 • Number of re-operations (excluding primary operation) 	Age 2-years corrected for preterm birth
Tertiary		

 • To determine if pHDM and Preterm Formula exert different effects on neurodevelopment through the mechanism of altered cerebral white matter microstructure 	
 • Cerebral white matter microstructure 	Term equivalent age (37-44 weeks postmenstrual age)

Title: COLLABORATE	EDGE No: 181495	Sponsor: Imperial College London	Version: 3.0; 09/01/2026
---------------------------	---------------------------	--	---------------------------------

 To establish if the additional cost of pHDM to the NHS is justified through a reduction in NEC 	
 Health resource use 	Neonatal unit discharge (or death)

 To establish if the additional cost of fortifier, generates savings through improved survival to age 2-years corrected for preterm birth without moderate-severe cognitive-language impairment 	
 Health resource use (subject to future funding) 	Age 2-years corrected for preterm birth

 To collect and store faecal samples from participants recruited in Edinburgh who are enrolled in randomisation 1, for future mechanistic studies 	
 N/A subject to future funding 	N/A

Title: COLLABORATE	EDGE No: 181495	Sponsor: Imperial College London	Version: 3.0; 09/01/2026
---------------------------	---------------------------	--	---------------------------------

3 STUDY DESIGN

3.1 Design

An efficient, UK-wide, adaptive, real-world-data-enabled, digital technology-facilitated, multicentre, 2-randomisation, open-label, controlled trial embedded in routine clinical care. The study includes an internal pilot to assess rates of recruitment, co-randomisation, and withdrawal of consent, and includes formal interim efficacy monitoring. See Study Flow Chart, Appendix 1.

The study involves two randomisations. In randomisation 1, we will compare the benefits of supplementation with either pHDM or Preterm Formula if the available volume of Own Mother's Milk is insufficient to meet her baby's needs. In randomisation 2 we will assess the benefits of routine versus no routine fortification of human milk; rescue fortification is permitted at the discretion of the attending clinician if a baby meets pre-defined criteria (see section 5.6.2).

3.2 Mechanistic study

3.2.1 Encephalopathy of prematurity

COLLABORATE includes an embedded mechanistic sub-study led by Co-I [name] that will use magnetic resonance imaging (MRI) to determine whether pHDM and Preterm Formula have different effects on cerebral white matter maturation, the hallmark feature of encephalopathy of prematurity, and hence impact the development of brain networks that underpin cognition. We will explore the potential differential effects of the interventions on cortical morphology and microstructure. This sub-study will involve 120 infants participating in COLLABORATE from the Royal Infirmary of Edinburgh. They will undergo 3T brain MRI using a research-dedicated, Wellcome-funded, brain-optimised Siemens MAGNETOM Prisma 3T scanner and 16-channel phased-array paediatric head and neck coil.

3.2.2 Gut microbiota

The gut microbiota is thought to play a role in human health and disease, including child development (24); it is modified by age at birth, sex, mode of delivery, antibiotic exposure, and feed type. The microbiome may mediate interactions of the gut-brain axis, including in preterm infants (25-27). For infants enrolled in the mechanistic study in Edinburgh, faecal samples will be collected at enrolment and weekly to 34 weeks. Samples will be processed and stored at -80°C in the Centre for Reproductive Health at the University of Edinburgh for later analyses subject to ethics approval and funding, exploring mechanisms linking nutritional exposures to brain development through gut-brain interactions.

3.3 Cost-effectiveness study

COLLABORATE embeds a within-trial economic evaluation, led by Co-I [name], to establish value for money of pHDM versus preterm formula, due to the large cost difference between the two interventions (up to £200 per litre for pHDM versus £5 per litre for formula) and the high costs of NEC treatment. The principal cost-effectiveness hypothesis for randomisation 2 (which will be subject to additional funding) is: In babies born <29 weeks gestation (P) who receive routine (I) versus no routine (C) fortification of human milk feeds, the additional cost of fortifier, generates savings through improved survival to age two-years corrected for prematurity without moderate-severe cognitive-language impairment (PO).

Title: COLLABORATE	EDGE No: 181495	Sponsor: Imperial College London	Version: 3.0; 09/01/2026
---------------------------	---------------------------	--	---------------------------------

4 STUDY SETTING AND PARTICIPANTS

4.1 Study setting

This study will recruit from approximately 80 Neonatal Intensive Care Units and Local Neonatal Units in England, Scotland, Wales, and Northern Ireland. As per standard practice for neonatal care across the UK, all other units across the country will be opened as continuing care sites (up to approximately 190 sites in total).

4.2 Inclusion and exclusion criteria

4.2.1 Randomisation 1

4.2.1.1 Inclusion criteria

- Born <29 weeks gestation
- No condition precluding enteral feeding
- Maternal intention to express breast milk
- Parent verbal consent

4.2.1.2 Exclusion criteria

- Baby has already received pHDM or Preterm Formula

4.2.2 Randomisation 2

4.2.2.1 Inclusion criteria

- Born <29 weeks gestation
- No condition precluding enteral feeding
- Maternal intention to express breast milk
- Parent verbal consent

4.2.2.2 Exclusion criteria

- Baby has already received Fortifier

4.2.3 Mechanistic sub-study

4.2.3.1 Inclusion criteria

- Participants in randomisation 1 recruited at the Royal Infirmary of Edinburgh
- Written parent consent

4.2.3.2 Exclusion criteria (MRI)

- Infants with congenital anomalies: structural or functional (e.g., metabolic disorders) that occur during intrauterine life and can be identified prenatally, at birth or later in life (WHO definition)
- Infants with a contraindication to MRI at 3Tesla

4.2.3.3 Exclusion criteria (stool sample collection)

- None

Title: COLLABORATE	EDGE No: 181495	Sponsor: Imperial College London	Version: 3.0; 09/01/2026
---------------------------	---------------------------	--	---------------------------------

4.3 Planned recruitment rate

There are currently 181 neonatal units in the UK; 55 are designated Neonatal Intensive Care Units (NICU) providing the highest level of care; 82 are Local Neonatal Units (LNU) providing intermediate care; and 44 are Special Care Baby Units (SCBU).

We aim to recruit from approximately 80 NICU and LNU, with the remaining units, including all SCBU, participating as step down sites which will continue randomised treatments and contribute outcome data. We will focus on maximising NICU participation as they admit about 70% of infants <29w gestation. We plan to open sites over the first 6 months. We based the recruitment site figure on a conservative assumption of 60% of NICU and LNU participation (i.e. 80 sites).

5 PROCEDURES AND MEASUREMENTS

5.1 Identification and recruitment of participants

Babies will be assessed for eligibility by a member of the clinical care team (an appropriately trained and experienced neonatal doctor or nurse) after admission to the neonatal unit. Parents must not have opted-out of their baby's data being included in the NNRD.

Cot cards and stickers for paper medical notes will be used to remind staff and parents about participation and to which intervention/s the baby is randomised. Cot cards and stickers will also contain a QR code which links to information on the COLLABORATE study website.

If electronic notes are used, a flag should be added to the participants record to identify their participation in the study.

5.2 Consent

5.2.1 Type and timing of consent

5.2.1.1 Main study

As this study compares interventions that are already in widespread use, verbal consent will be sought for the main study. This will be documented in the eCRF and medical/research records by the member of the clinical care team who has explained the study and sought consent. Verbal consent is well received by parents and clinicians and has been used in other RCT evaluating interventions that are already in wide use, including the current NIHR funded clinical trial of a medicinal product, BASE (ISRCTN 18260410).

The verbal consent statement will be completed by the participating site staff electronically in OpenClinica to aid central monitoring of consent data. A paper back-up version may be used where access to the OpenClinica database is not possible.

Participants will be provided with a copy of the Participant Information Sheet and completed verbal consent statement. Consent will be sought a time considered clinically appropriate and before the baby has received any supplemental feeds or fortifier.

Before discharge from the neonatal unit, a discussion will take place with parents to remind them that the trial team will contact them at 2 years to ask them to complete the Parent Report of Children's Abilities-Revised (PARCA-R) questionnaire. At discharge, parents will be asked to confirm their contact details are up to date to improve data return rates.

Title: COLLABORATE	EDGE No: 181495	Sponsor: Imperial College London	Version: 3.0; 09/01/2026
---------------------------	---------------------------	--	---------------------------------

5.2.1.2 Mechanistic sub-study

Parents will be approached to tell them about the MRI procedure and stool sample collection at a clinically appropriate time, and their written informed consent sought for their baby to take part. This is an optional sub-study, and not all babies recruited in the participating centre will take part.

5.2.2 Consent sought

5.2.2.1 For all participants

Verbal consent will be sought for:

- Randomisation 1
- Randomisation 2
- The results of the age 2-year Parent Report of Children's Abilities-Revised (PARCA-R) assessment to be included in the infant's National Neonatal Research Database record and hence available for other approved research studies
- Longer term follow-up using linkage of other routinely collected NHS and non-NHS data (e.g., Hospital Episodes Statistics; National Pupil Database) using the NHS number and other identifiers (subject to additional funding)
- Permission to forward study results to participating families
- Permission to use data obtained in COLLABORATE in future approved research studies
- Permission to recontact parent/guardians for future research

5.2.2.2 For babies participating in the mechanistic sub-study

Additional written consent will be sought for:

- Magnetic resonance imaging at term equivalent age (37-44 weeks)
- Permission to share anonymised MRI data with other researchers running research ethics approved studies subject to data access and collaboration arrangements governed by the University of Edinburgh
- Permission to collect weekly stool samples from birth to neonatal unit discharge and at time of MRI scan
- Permission to inform the General Practitioner of participation in COLLABORATE mechanistic sub- study
- Permission to use stool samples obtained in future approved research studies

5.3 Randomisation: timing and method

5.3.1 Timing

Babies may participate in either or both randomisations; see Flow Chart, Appendix 1.

Randomisation 1 to pHDM or Preterm Formula, will occur when the attending clinician decides a supplemental feed is required because the volume of Own Mother's Milk is insufficient.

Randomisation 2, to routine fortification or no routine fortification, will occur when the baby is receiving between 60-120 ml/kg/day of human milk feeds (Own Mother's Milk and/or pHDM). By "fortification" we mean immediate or incremental increase to "full strength fortification" according to neonatal unit practice. We refer to "no routine fortification" because rescue fortification is permitted (see section 5.6.2).

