1.4 Rationale for the study

The rationale for this study is that the types of enteral feeds an extremely preterm baby receives, namely fresh Own Mother's Milk, pHDM, Preterm Formula, and macronutrient fortifier, are widely believed to influence the risk of necrotising enterocolitis (NEC), and because nutrition, and the non-nutritional components of human milk are highly likely to affect the development of the preterm brain. However, pHDM, Preterm Formula, and macronutrient fortifier have entered into widespread use without evidence of efficacy or safety.

NEC is an acquired inflammation of the immature gastrointestinal tract and leading cause of death and life-long impairment in extremely preterm babies in high-income settings such as the UK. There are around 3000 babies born <29 weeks gestation, and around 260 NEC deaths and/or surgeries each year in the UK, with up to 3 times more developing less severe disease that nonetheless disrupts feeding, prolongs hospital stay, and increases antibiotic exposure, and costs of care (1).

Own Mother's Milk is standard of care for all newborn babies and reduces but does not totally prevent NEC (1). Own Mother's Milk and pHDM are not equivalent as not only is human milk very variable in nutrient and non-nutrient content, but composition is unique to each mother, and pasteurisation substantially reduces or destroys biologically active non-nutritional components (2).

The developmental ability to suckle effectively is not reached until 33-34 weeks postmenstrual age, hence mothers delivering preterm must express breast milk for many weeks which they report as stressful and difficult to sustain. Therefore, over 85% of extremely preterm babies require supplementary feeds because a mother is unable to express sufficient milk to meet her baby's needs. Often, the shortfall is only temporary. Overall, in the UK, around a third of extremely preterm infants requiring supplementary feeds receive pHDM and around two-thirds receive Preterm Formula (3).

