2.4 Endpoints

2.4.1 Primary

Assessed at 34 weeks postmenstrual age

- Survival without surgical NEC

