7.2 Sample size and power

7.2.1 Main study

This is a group-sequential trial with 2 interim and 1 final analysis (i.e., an adaptive trial), hence the sample size is not fixed. The maximum sample size is 3252, (n=2168 in each randomisation; n=1084 per arm) assuming no early stopping, estimated on the composite primary efficacy outcome (survival to 34 weeks gestational age without surgical NEC (Y/N)).

Title: COLLABORATE	EDGE No: 181495	Sponsor: Imperial College London	Version: 3.0; 09/01/2026
---------------------------	---------------------------	--	---------------------------------

For the randomisation 1 (pHDM vs Formula supplement) an observational analysis of NNRD data estimated the difference in the proportion surviving to 34w PMA for babies born <29 weeks' gestation to vary between 0.18 and 0.52 depending on week of gestational age (favouring supplementation with preterm formula) (6) For the sample size calculation we targeted a highly conservative MCID in this proportion of 0.05 based on a baseline of 0.82 which we accurately estimated from the NNRD for this population of babies in the UK (i.e. from 0.82 to 0.87).

For randomisation, 2 (fortifier vs no routine fortifier) an unpublished observational analysis from NNRD data estimated the difference in proportion data surviving to 34w PMA for babies born <29 weeks gestation to vary between 0.06 and 0.75 depending on week of gestational age (favouring fortifier). Taking a conservative approach and in line with the first comparison, we have chosen to target the same MCID of 0.05.

We have calculated power based on a fixed sample size of 3252 unique babies using rpact (33) where interim timings were chosen to minimise the expected sample size. We anticipate at least 50% of babies will be co-enrolled into both randomisations. If co-enrolment is higher, power will increase. We have used an O'Brien & Fleming design with two-sided overall significance level of 5% to account for two interims at 50% and 75% and a normal approximation assumption for rates. For both randomisations we have factored in 2% missing outcome data due to carers withdrawing consent from routine data collection in NNRD.

Based on all the above assumptions, n=3252 (n=2168 in each randomisation and n= 1084 per arm) will achieve a minimum of 87% power for each randomisation. The expected sample size across for each randomisation is n=2439.

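### Neither randomisation requires the 34-week outcome to be still open at entry, so babies whose primary outcome is already decided can be randomised; the dilution is probably small but cheap to prevent

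*Protocol*

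**What the plan says.** The primary endpoint (Protocol 2.4.1) is "Survival without surgical NEC", assessed at the fixed point of 34 weeks postmenstrual age.

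The inclusion criteria are the same for both randomisations (4.2.1.1 and 4.2.2.1): birth before 29 weeks, nothing that rules out enteral feeding, a mother who means to express, and verbal consent. Each randomisation has one exclusion: "Baby has already received pHDM or Preterm Formula" for the first (4.2.1.2) and "Baby has already received Fortifier" for the second (4.2.2.2).

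On timing, section 5.3.1 states that "Randomisation 1 to pHDM or Preterm Formula, will occur when the attending clinician decides a supplemental feed is required". The second randomisation is triggered by an intake of 60 to 120 ml/kg/day of human milk, and is not limited to the first time that intake is reached. Neither trigger carries a latest postnatal or postmenstrual age.

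Three other places presume early entry without requiring it. The schedule in 5.5 puts randomisation in the admission column, but its footnote refers back to the eligibility criteria. The safety window in 6.7 runs from randomisation to 34 weeks at the latest. Section 7.3 treats the two randomisations as near each other in time.

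Section 7.1 bases the analysis on the intention-to-treat population. Section 7.2.1 states that the design "will achieve a minimum of 87% power for each randomisation" for a change in the primary outcome "i.e. from 0.82 to 0.87", and allows only for 2% of outcomes lost through withdrawal of consent.

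**The concern.** Two kinds of baby can enter with the primary outcome already settled.

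- **Past 34 weeks.** Section 1.4 says that "mothers delivering preterm must express breast milk for many weeks which they report as stressful and difficult to sustain", so a shortfall of mother's milk can come late. A baby fed only on own mother's milk until then has had neither study supplement and still qualifies for randomisation 1. If alive without surgical NEC at 34 weeks, that baby is a certain success.
- **Earlier surgical NEC.** Section 1.4 also says that own mother's milk does not prevent all NEC. The feeding criterion keeps out a baby who cannot be fed now, but not one who has recovered and is being re-fed. If the baby has not had the relevant study product, either randomisation is open, and the baby enters as a certain failure.

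For these babies the true treatment effect on the primary outcome is zero. The treatment-policy estimand in 7.1 does not justify keeping them, because it concerns events after randomisation and these came before. Surgical NEC is also a secondary endpoint (2.4.2) and a safety event of special interest (7.7), so an operation that preceded allocation would be tabulated by arm. At stake are a diluted effect estimate, some power, and a clean count of surgical NEC.

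**Working it through.** **Inputs.** Rates 0.82 and 0.87 (7.2.1). Critical values 2.863, 2.337 and 2.024 at 50%, 75% and 100% (7.4). Numbers: 2168 per randomisation less 2% is 2168 × 0.98 = 2125. The table in 7.4 ends at 2126 for randomisation 2 (1063 per arm) and 1908 for randomisation 1 (954 per arm), reading its entries as totals over both arms. Why those totals differ is a separate matter, so both are carried. The share f of randomised babies with a fixed outcome is not in the protocol and is an assumption.

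**Step 1: reproduce the design.** The variance term is v = 0.82 × 0.18 + 0.87 × 0.13 = 0.2607. The standardised difference at the final look is θ = 0.05 / √(v/n).

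- n = 1063 per arm: θ = 0.05 / 0.01566 = 3.193
- n = 954 per arm: θ = 0.05 / 0.01653 = 3.025

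Integrating the three-look trivariate normal distribution over the stated limits gives an overall two-sided error of 0.050 under no effect. Power is 88.5% at 1063 per arm, in line with the stated minimum of 87%, and 84.9% at 954 per arm.

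**Step 2: dilute.** If a share f cannot respond to allocation, the expected intention-to-treat difference is D = (1 − f) × 0.05. Section 7.2.1 takes 0.82 from national data on this population, so the overall control rate stays at 0.82 and the other arm becomes 0.82 + D.

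| f (assumed) | D | θ, 1063 per arm | Power | θ, 954 per arm | Power |
|---|---|---|---|---|---|
| 0% | 0.0500 | 3.193 | 88.5% | 3.025 | 84.9% |
| 1% | 0.0495 | 3.159 | 87.8% | 2.992 | 84.1% |
| 2% | 0.0490 | 3.124 | 87.1% | 2.960 | 83.3% |
| 5% | 0.0475 | 3.022 | 84.8% | 2.863 | 80.8% |

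On this basis power reaches 80% at f of about 10.5% (1063 per arm) or 5.9% (954 per arm).

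**Step 3: how large can f be?** For earlier surgical NEC, section 1.4 gives a rough ceiling: about 260 NEC deaths and/or operations a year among about 3000 births below 29 weeks, or 260/3000 = 8.7%. A share of 2% would need 2/8.7 = 23% of all those events to be operations before randomisation in babies who survived, were fed again and were still eligible. A share of 5% would need 5/8.7 = 57%. For entry after 34 weeks the protocol gives no figure. In randomisation 2 the intake trigger describes feed build-up, which makes that route less likely.

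**The case against.** The strongest reply is that this hardly matters. The feeding criterion keeps out active disease, the protocol plainly expects early randomisation, and at 1% to 2% the power at 1063 per arm is still at or above the stated 87%. Broad eligibility also suits a trial embedded in routine care, and late entrants would still inform survival to discharge and the 2-year outcomes. A 34-week limit is only partial too, since a baby one day short of it is almost as settled. Most of this stands as an argument about size. It does not close the gap: the expectation of early entry is not an eligibility rule, and babies kept for later outcomes need not be in the primary analysis.

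Two stronger readings are tempting and not supported.

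- **That power falls below 80%.** A reader could treat earlier surgical NEC as extra failures that multiply both rates by (1 − f). At 1063 per arm that gives 84.3% at 2% and 77.8% at 5%. But 7.2.1 presents 0.82 as the national rate for this population, which on its face already contains surgical NEC whenever it occurred. Lowering it again counts those failures twice, and Step 3 makes 5% implausible.
- **That the comparison is biased for or against one arm.** The events precede allocation, so randomisation balances them on average. The harm is dilution and noise. The error rate under no effect is untouched.

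**Conclusion.** The concern holds in a limited form. As written, both randomisations admit babies whose 34-week outcome allocation cannot change, and the analysis keeps them. Entry after 34 weeks is mainly an issue for randomisation 1; earlier surgical NEC can affect either.

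The likely cost is modest: about 0.7 to 1.4 percentage points of power at 1% to 2% with 1063 per arm, and 3.7 points at 5%. Randomisation 1 has less room if 954 per arm is the working figure, reaching 80.8% at 5%. These sizes rest on an assumed f, on an overall control rate of 0.82, and on no effect at all in the fixed babies. Counting surgical NEC that preceded allocation in the primary, secondary and safety comparisons is a fault whatever its frequency. The point is worth correcting because the correction is simple, not because the design fails without it.

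**What to change.** Add to the eligibility of both randomisations, and check in the randomisation form, that the primary outcome is still undetermined: the baby has not reached 34 weeks postmenstrual age and has had no surgical NEC. This takes two lines of text and two form checks. The cost is that a few babies no longer contribute to the discharge and 2-year secondary outcomes.

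If the team prefers to keep them for those outcomes, define the primary analysis set as babies whose outcome was undetermined at randomisation. That restriction uses only information from before allocation, so it does not break the randomised comparison. Surgical NEC that preceded randomisation should then be recorded as a baseline feature and left out of the secondary and safety counts.

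If neither is adopted, state why such babies are included and allow for them. Holding information constant needs roughly 2168 / (1 − f)² babies per randomisation: 2168 / 0.9604 = 2258 at 2%, or 2168 / 0.9025 = 2403 at 5%. That is far dearer than the eligibility lines.
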